High-gamma amplitude will be calculated using an approach that utilizes the Hilbert transform. Specifically, the signal will be filtered into 8 subbands, logarithmically spaced between 70-150 Hz. For each subband, we will calculate the amplitude (absolute value) of the analytic signal, which is estimated using the Hilbert transform. Each subband will be normalized to its baseline mean and standard deviation, estimated across trials. The HGA estimate is then the mean across these subbands.

We will use *least-squares linear regression neural encoding models* to investigate relationships between acoustic stimulus dimensions and STP neural responses during the baseline quiet context, in which stimuli sample a 2-d F0 x VOT grid. This approach will allow us to identify the subset of electrodes and temporal windows that encode at least one of these 2 dimensions at baseline; targeted analysis on this subset (described below) will then be used to compare listening contexts.

Encoding model inputs will consist of F0 and VOT, with an output of channel- and time-specific HGA. For a given electrode, individual models will be built using single trial data and a sliding window, allowing us to identify the temporal window relative to stimulus onset that yields significant models. Model quality will be assessed in two ways. First, using models built on all trials, we will calculate the regression *F*-statistic, which determines if any coefficients are significant. This will be compared to null distributions estimated with permutation tests that shuffle data across trials. Second, goodness-of-fit will be assessed for significant models by performing leave-one-out cross-validation and calculating R^2 , the proportion of variance in neural activity explained by the model. Finally, we will assess the relative encoding strength of each acoustic dimension using model coefficient *t*-statistics. In summary, this approach will allow us to identify the timing and anatomical location of F0 and VOT encoding during baseline quiet listening conditions for which dimensions are sampled orthogonally (as in **Figure 1a**).

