To characterize shifts in neural encoding across listening contexts, we will investigate Noise using encoding models and Canonical/Reverse contexts using *cluster-based approaches*.^{32,49} Encoding models will be built from the Noise context for all channels and timepoints, using the same approach as Baseline. If a channel/timepoint is significant in either Baseline or Noise, the F0 and VOT coefficient *t*-statistics will be compared across contexts. We hypothesize that encoding of F0 will strengthen and VOT will weaken in Noise, as measured by changes in *t*-statistic magnitudes across multiple models. Next, we will compare neural responses for each of the two *Test* stimuli (which were embedded in the F0 x VOT grids, **Figure 1a**) between Baseline vs. Canonical and Canonical vs. Reverse. The clustering approach will look only at Baseline significant channels and time windows and involves randomly assigning listening context labels to single-trial data followed by a *t*-test at each time step. Across all permutations, a criterion value will be established for each timepoint (>95% of absolute value of *t*). For each of these permutations, we will next determine whether its value exceeds criterion across timepoints, and for how many timepoints it exceeds criterion (a 'cluster'). For each cluster, *t* values will be summed and assigned to all points in the cluster, with the largest summed cluster value stored for each permutation. This will create a null distribution of 1000 cluster values. We then will establish whether the cluster size calculated across real neural data (organized according to listening context) exceeds the 95% permutation-based cluster values such that $p < .001$ indicates an observed cluster is greater than all permutation-based clusters. Using this approach, we will identify context-dependent shifts in HGA responses, which we predict will reflect observed shifts in perceptual weights. Namely, we hypothesize that HGA responses in F0-encoding channels will be enhanced in the Canonical context relative to both Baseline and the Reverse context.

Rigor and Reproducibility. Analyses will be controlled for multiple comparisons, with sex as a co-variate in our analyses. We will use pre-registration and provide access to all the deidentified source data.

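### Noise and Baseline encoding are compared at sites chosen by the same fits, with no selection-aware test, so site-level gains and losses of F0 encoding are unreliable at null or weak sites

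*SAP*

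**What the plan says.** All of this is in the SAP under Evaluating the Hypotheses: Neural Analyses.

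- Screening: "First, using models built on all trials, we will calculate the regression *F*-statistic, which determines if any coefficients are significant". The F statistic is referred to a permutation null.
- Noise: "Encoding models will be built from the Noise context for all channels and timepoints, using the same approach as Baseline".
- Measure of encoding: "we will assess the relative encoding strength of each acoustic dimension using model coefficient *t*-statistics".
- Comparison: "If a channel/timepoint is significant in either Baseline or Noise, the F0 and VOT coefficient *t*-statistics will be compared across contexts".
- Hypothesis: "We hypothesize that encoding of F0 will strengthen and VOT will weaken in Noise", to be judged "as measured by changes in *t*-statistic magnitudes across multiple models".
- Cross-validation enters only afterwards: "goodness-of-fit will be assessed for significant models by performing leave-one-out cross-validation". It does not separate selection from comparison.

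No unit of analysis, test, reference distribution or alpha is given for the change in t. By contrast, the Canonical/Reverse comparison has a context-label permutation null. Rigor and Reproducibility promises multiplicity control without naming a method or a family. Earlier in the same section, the subset to be used for comparing contexts is defined from Baseline alone, which differs from the either-context rule for Noise.

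**The concern.** A site enters the comparison because its F statistic was large in at least one context, and F is built from the t statistics that are then compared. Keeping a pair of numbers because one of them is large tends to make their difference large. A site that passes only in Noise will look as if it gained encoding, and one that passes only in Baseline as if it lost it, even if nothing changed.

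H3 (the shift in noise) is read from these changes. H6 and H7 ask where in the cortical hierarchy plasticity appears, which invites a map of individual sites. False gained and lost sites on that map would bear directly on those hypotheses.

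**Working it through.** **Plan's own figure.** The SAP gives no error rate for this comparison, so there is none to reproduce. N=25 concerns behavioral effects and does not enter here.

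**Inputs from the SAP.** Two predictors (F0, VOT), sampled orthogonally at Baseline; joint F on all trials; either-context selection; comparison of coefficient t statistics.

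**Assumptions, not in the documents.** 200 trials per context, so df = 200 − 3 = 197; the same grid and equal trials in both contexts; screen at .05 or .001; true F0 signal 0–1 and VOT 0–2 standard errors (SE) for null or weak sites.

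**Step 1: how the kept sites arise.** With orthogonal predictors, F = (t_F0² + t_VOT²)/2. For a null site at a .05 screen, P(kept) = 1 − 0.95² = 9.75%. The share of these significant in one context only is (2 × 0.05 × 0.95)/0.0975 = 97%.

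**Step 2: hand check.** In large samples 2F is chi-square on 2 df with 5% point 5.99. Given that it exceeds 5.99, its mean is 5.99 + 2 ≈ 8, so t_F0² averages about 4 in the context that selected the site and about 1 in the other. The variance of the difference is then about 5 instead of 2. A test calibrated to variance 2 rejects at P(|Z| > 1.96/√2.5) = P(|Z| > 1.24) ≈ 21%. Simulation gives 24%, because the selected distribution is not normal.

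**Step 3: simulation.** At least one million sites per setting with no true change, and a signed test of the F0 difference whose level without selection is 5%:

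| True F0, VOT (SE) | .05 screen | .001 screen |
|---|---|---|
| 0, 0 | 24% | 47% |
| 1, 0 | 15% | 45% |
| 1, 1 | 10% | 26% |
| 0, 2 | 7% | 11% |
| 1, 2 | 6% | 12% |
| 2, 2 | 5% | 10% |
| 3, 0 | 5% | 10% |
| 4, 0 | 5% | 6% |
| 3, 3 | 5% | 5% |

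A test of the change in |t|, closer to the SAP's wording, rejects 30% (.05) and 56% (.001) at null sites. Across the null and weak settings, Noise-only sites show a mean rise in F0 |t| of about 0.3–1.4 at the .05 screen; Baseline-only sites show the mirror-image fall.

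**Step 4: mixed sets and multiplicity.** In sets of 1,000 sites (.05 screen) where 0, 10 or 30% encode at 3 SE, the signed test rejects at 24, 14 and 9% of selected sites. Bonferroni counted over selected sites only leaves a familywise error of 41, 26 and 13%.

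**Step 5: the average over selected sites.**
- No change in either dimension: mean F0 change about 0, test level about 5% (sites independent).
- F0 unchanged at 0–1 SE, VOT falling from 2 to 0.5: mean F0 |t| change about −0.09 (.05) or −0.3 to −0.5 (.001); without selection it is 0.
- F0 rising from 1 to 2, VOT falling from 2 to 1: 0.97–0.98 against 0.85–0.86 unselected (.05), an upward bias of about 0.12.
- Baseline-only selection, no change: in sets of 200 or 1,000 sites the averaged test rejects 61–100% at a .05 screen, towards an apparent F0 loss.

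**Step 6: remedies under no change.** Pooled selection with a signed difference test rejects about 5–6%. It does not repair a |t|-difference test, which still rejects about 16–17% at null sites (.05 screen). Repeating the either-context selection inside each permutation gives about 3–6% for the |t| change.

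**The case against.** The strongest reply is that the SAP specifies no per-site 5% test. It words the hypothesis as a change in magnitude across many models. If that means an average over selected sites, the either-context rule is symmetric, and with nothing changing the average is unbiased and its test holds its level. This stands, within limits: it assumes independent sites, which overlapping sliding windows are not, and it fails once one dimension changes. A fall in VOT encoding is itself part of the stated hypothesis.

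A second reply is that the SAP reports pilot high-gamma activity modulated by VOT and F0 across STP electrodes, so null sites need not dominate. This also stands in part. With a .05 screen, inflation is negligible at sites encoding at about 3 SE or more. But models are screened at every channel and time point, and a strict screen is plausible given the promise of multiplicity control. At .001, a site at 3 SE for F0 with VOT null still rejects about 10%.

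Third, the either-context rule has a purpose: it retains sites that encode in one context only. This is a real cost of pooled selection, and a reason to offer a second route.

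**Conclusion.** The circularity is in the stated rule and is not merely a missing detail. Its harm is confined to particular uses: per-site claims at null or weakly encoding sites (about 6–24% rejection with a .05 screen, 11–47% with .001, against a nominal 5%), and averages when encoding of either dimension changes. These sizes rest on the assumed trial numbers, signal range and screening levels. The SAP gives none of these.

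Three stronger readings are tempting and not supported. A reader might infer that the Noise comparison as a whole has an inflated error rate; it does not at clearly encoding sites with a .05 screen, nor for an average when nothing changes. A reader might infer that a site map would be mostly selection; in the mixed sets the per-site rate falls to 14% and 9% as the share of encoding sites rises to 10% and 30%. A reader might infer that selection works against H3; the bias is downward if only VOT falls, but upward in the example where F0 rises and VOT falls together, as the SAP predicts.

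**What to change.** In the Noise paragraph of the SAP, name the unit and the test, and make the test valid given the selection by one of two routes.

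(a) Fit one model per channel and time window to Baseline and Noise trials together. Select on the pooled F0 and VOT slopes, then test the signed context × F0 and context × VOT interactions instead of a |t| difference. The level of about 5–6% needs equal trial numbers, the same stimulus grid and similar residual variance in both contexts. Cost: sites that encode only in Noise are kept clearly less often. For F0 going from 0 to 3 SE with VOT null, retention falls from 78% to 46% (.05) and from 27% to 8% (.001). Sites with stable encoding are kept more often; for F0 at 3 SE in both contexts, retention at .001 rises from 47% to 72%.

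(b) Keep the either-context rule and the |t| change, and repeat the whole selection inside every context-label permutation. Cost: more computation and a slightly conservative test.

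Either way, state the multiplicity method and its family, and say whether the Baseline-only subset described earlier in the section or the either-context rule governs the Noise comparison. No new data are needed.

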### 2. Describe and explain the study design:

This experimental study uses a within-subjects design.

All enrolled participants will be implanted with sEEG electrodes in the auditory cortex based on clinical necessity. During the post-operative period, patients will complete self-paced blocks of trial stimuli by listening to sound via earphones and making behavioral, categorical decisions about speech sounds, duration of stimuli, and pitch of stimuli. Simultaneous sEEG and scalp EEG recordings will be obtained to record neural responses to stimuli.

Participants will first complete a block of stimuli for clear speech to establish a baseline. They will then complete blocks of stimuli with experimental manipulations. All blocks will consist of intermixed exposure trials and test stimuli. Each participant will complete all tasks provided they are willing to do so and that their medical status permits.

Auditory stimuli used in this part of the study are part of the dimension-based statistical learning (DBSL) paradigm developed and extensively tested by [name] in previous research.

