### 3. Provide a description of the following study timelines:

#### Duration of an individual subject's active participation:

Participants will continue to be enrolled in the study for the duration of their sEEG implantation in the EMU. This period of time may range from 3-10 days post-operatively until the participant completes all research tasks, indicates that they would like to disengage from research activities, or is taken back to the operating room for removal of electrodes.

Each participant will have active participation in the study for only the amount of time per day that they voluntarily desire participating. Blocks of stimuli are self-paced and the research team will offer breaks between blocks as needed or requested by the participant.

Based on previous research with similar protocols and stimulus paradigms, we anticipate that a subject may complete all research tasks over a cumulative period of 2-3 hours. This includes equipment setup and removal.

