Official Study Title:

Flexible representation of speech in the supratemporal plane

NCT Number:

NCT05209386

Document:

Statistical Analysis Plan

Document Date:

July 15, 2020

STATISTICAL DESIGN AND POWER ANALYSIS

Statistical Design, Power and Analytic Approach. We will test neurosurgical patients (ages 15-25 years) undergoing evaluation and treatment who require chronic (>7 d) sEEG implantation and recording of the temporal lobe for seizure localization or brain mapping. One set of behavioral tasks, and corresponding electrophysiological measures, will allow us to address Aim 1. Another will address Aim 2. Patient permitting, our goal is to have the same patient complete all tasks. All participants will undergo neuropsychological tests and will have detailed history/demographic information as part of their clinical battery.

Power and Sample Size. Robust behavioral effects will allow examination of perceptual weights in neural representation. Using behavioral effect sizes from **Figure 2** pilot data to estimate the sample size required for a predicted power of 0.8 (two-tailed alpha at .05) yields a sample of N=25. This leaves open the issue of power for neural measures. Our pilot EEG data with the same task/stimuli revealed robust effects with N=23 (**Figure A**), reassuring that N=25 is a reliable target for EEG. The SNR advantages of sEEG versus EEG, and our sEEG pilot data in **Figure 3**, suggest that this sample size will be more than sufficient for sEEG measures, especially as they will be utilized in a within-patient/within-electrode experimental design.

Analyses. Specific pre-registered analyses will assess the hypotheses outlined in the Approach section of the proposal. Specifically, we will test the following hypotheses:

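### The Noise effect (H3) is measured by a change in |t|, which also depends on trial count, so fewer usable Noise trials could hide a modest F0 rise

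*SAP*

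**What the plan says.** The SAP (Evaluating the Hypotheses: Neural Analyses) regresses high-gamma activity (HGA) on F0 and VOT by least squares, separately for each electrode and time window, using single trials and all of them. At baseline, "we will assess the relative encoding strength of each acoustic dimension using model coefficient" t-statistics. Noise models are then built in the same way from the Noise trials. The comparison rule is: "If a channel/timepoint is significant in either Baseline or Noise, the F0 and VOT coefficient" t-statistics are compared between contexts. The prediction is "encoding of F0 will strengthen and VOT will weaken in Noise, as measured by changes in" t-statistic magnitudes.

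On normalisation the SAP says: "Each subband will be normalized to its baseline mean and standard deviation, estimated across trials". It does not say whether that reference is set once or separately for each context.

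On how much data each context will have, Protocol Study Design item 2 says: "Participants will first complete a block of stimuli for clear speech to establish a baseline". It adds: "Each participant will complete all tasks provided they are willing to do so and that their medical status permits". Under item 3, participation runs until the participant "completes all research tasks, indicates that they would like to disengage from research activities, or is taken back to the operating room". The SAP's opening section puts it this way: "Patient permitting, our goal is to have the same patient complete all tasks". Protocol Research Activities item 1 makes the sessions self-paced and dependent on the patient's schedule, health and motivation.

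Neither document gives trial counts per context, a minimum number of trials, a matching rule, or a formal test for the change in t.

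**The concern.** A coefficient t-statistic measures how precisely an effect is estimated, so it mixes the strength of encoding with the amount of data. Inside one model this does no harm to a comparison of F0 with VOT, because both use the same trials. Across two separately fitted models that protection is lost.

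The SAP's other safeguards do not reach this contrast. The F-statistic permutation test asks whether a model encodes anything at all. Leave-one-out R² describes the fit of the whole model. The permutation of context labels covers only the Baseline, Canonical and Reverse comparisons. The behavioural accent analysis does use a block-by-F0 interaction, but the neural Noise contrast has no counterpart.

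At stake is H3, a named directional hypothesis. If Noise has fewer usable trials, a modest true F0 rise may shrink, vanish or reverse on the |t| scale, and VOT may seem to weaken with no true change.

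**Working it through.** **Plan's own figure.** N=25 (power 0.8, two-tailed alpha .05) rests on a behavioural effect in a figure that is not shown, so it cannot be reproduced. For a paired comparison it would imply a standardised effect of about (1.960 + 0.842)/√25 = 0.56. It does not enter this point, which concerns trials per context.

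**Scaling.** With orthogonal F0 and VOT, t ≈ b × SD(x) × √n / σ. For fixed b and σ, and r = Noise trials / Baseline trials:
- ratio of |t|, Noise to Baseline = √r
- true rise that is exactly cancelled = 1/√r - 1

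| r | √r | Fall in t magnitude | Rise cancelled |
|---|---|---|---|
| 0.90 | 0.949 | 5% | 5% |
| 0.75 | 0.866 | 13% | 15% |
| 0.50 | 0.707 | 29% | 41% |

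Example: a true F0 rise of 20% shows as 1.20 × 0.866 = 1.04 at r = 0.75 (+4%), and as 1.20 × 0.707 = 0.85 at r = 0.50 (-15%).

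**Check on simulated trials.** Assumed: 5×5 grid, 200 Baseline trials, F0 0.20, VOT 0.40, residual SD 1, 4000 runs. With no true change and 100 Noise trials, mean VOT |t| falls from 5.68 to 4.03 (ratio 0.71), while the mean coefficient stays at 0.40. A true 25% F0 rise gives mean |t| of 3.52 at equal trials but 2.54 at half the trials, against 2.86 at Baseline.

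**Consequence across patients.** The documents give no trial counts or neural effect sizes, and the SAP names no test here, so every input is assumed: 25 patients, 6 channels each, 7×7 grid, 196 Baseline trials, F0 0.30, VOT 0.60, residual SD 1, between-patient SD of the change 0.05, true VOT change -20%. The assumed test is a one-sample t across patients, two-sided 5%, with both shifts required. Ranges are across runs.

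| Noise trials relative to Baseline | Detection by change in t magnitude, F0 +20% | F0 +30% |
|---|---|---|
| Equal | 99% | 100% |
| Varying 75-125% between patients | 98% | not given |
| 20% of patients at 75% | 94-95% | 100% |
| 20% of patients at 50% | 68-74% | 99% |
| 40% of patients at 50% | 13-17% | 73% |
| All at 90% | 87-89% | 100% |
| All at 75% | 14-16% | 84-87% |
| All at 50% | 0% | 0% |

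With all patients at 75%, trial-matched |t| detects 98% (F0 +20%) and 100% (F0 +30%), and the coefficient change 99% and 100%. For F0 +50%, |t| still detects 100% at that ratio. Over 18 sets of inputs with all patients at 75% and F0 +20%, |t| detects 8-38% and the coefficient change 30-100%.

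**No true change.** The full pattern (F0 up and VOT down) appears in at most 0.1% of runs by either measure. VOT weakening, read alone, appears by |t| as follows:
- All patients at 90% / 75% of trials: 63-66% / 100% with VOT 0.60; 34% / 99% with VOT 0.40; 5% / 23% with VOT 0.20 and between-patient SD 0.10.
- Only 20% of patients at 75%: 6-20% with VOT 0.30-0.60.
- By coefficient, base inputs: 2-3%, close to the nominal 2.5%.

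**The case against.** The strongest reply is that the documents never say Noise will be short of trials. The protocol expects all tasks to take 2-3 hours in total, spread over a stay of 3-10 days with breaks, and both documents intend full completion. A patient who stops between blocks might contribute no Noise data, and so no contrast, rather than a partial block. What the protocol supports is stopping that differs between patients, not one deficit shared by all 25. This stands, and it is why the rows with partial deficits matter most. It does not remove the concern: clear speech comes first, so early stopping costs later-block trials and the losses need not average out.

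A reader might infer that the measure could falsely confirm H3. The documents do not support that. The prediction is crossed, whereas a shortage of trials moves both |t| values the same way. Only the VOT half can be imitated by a shortage, and the rates for that depend heavily on the assumed inputs.

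A reader might also infer that |t| must be abandoned. That goes too far. At equal trials it performs well, and with weak F0 encoding (0.15, between-patient SD 0.10, F0 +20%) it detects more than the coefficient change, 43% against 33%.

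The SAP refers to pre-registered analyses, a proposal and a pilot pipeline, any of which may fix trial counts or matching; none is in the documents. The SAP also predicts better-differentiated HGA to the Test stimuli in Noise than in clear speech, but it assigns the Noise comparison to the encoding models.

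**Conclusion.** The concern holds in a limited form. As written, the Noise comparison depends on trial count, and nothing stated in the plan corrects for that. The square-root scaling follows from least squares, with coefficient and residual SD held fixed, and does not depend on the assumed effect sizes. The practical harm is mainly lost sensitivity to a modest F0 rise, and a misleading VOT result if that half is read alone.

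The size turns on how common and how deep any shortage is. It is small if trials are equal, if imbalance is balanced across patients, if few patients are affected, or if the F0 effect is large. It is severe if a deficit is common. Every detection rate rests on assumed trial counts, effect sizes and an across-patient test that the SAP does not name. This is worth correcting before analysis, with medium confidence, because unequal trials are plausible but not stated.

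**What to change.** In the SAP's Noise paragraph, make the Baseline-Noise comparison independent of trial count.

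- **Simplest form, keeping the SAP's measure:** for each patient and channel, repeatedly subsample the context with more usable trials down to the other's count, balanced over the F0 × VOT grid, and compare |t| on the matched sets.
- **Alternative or supporting analysis:** fit one trial-level model to both contexts with context-by-F0 and context-by-VOT terms, using one HGA normalisation common to both.
- **Decision rule and reporting:** require both the F0 increase and the VOT decrease before H3 is called supported, and report usable trials per context and patient.

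The cost is SAP wording, a little re-analysis and some precision lost with discarded trials; no new data are needed. Matching does not remove the dependence of |t| on residual variance: in the simulated trials above, a residual SD 25% higher in Noise, with equal trials and unchanged coefficients, lowers mean VOT |t| from 5.68 to 4.57. The coefficient version has its own limits. It depends on the common normalisation: if HGA is normalised per context and Noise residual SD is 25% higher, simulated detection is only 0.1% for F0 +20% and 17% for F0 +30%, no better than |t|. It can also detect less than |t| at equal trials when encoding is weak.

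### No neural context effect is tested across patients: the tests described support claims about single channels, not the general hypotheses

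*SAP*

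**What the plan says.** - **Sample size** (SAP, Power and Sample Size). The number of patients comes from behaviour: "Using behavioral effect sizes from Figure 2 pilot data to estimate the sample size required", so that "a predicted power of 0.8 (two-tailed alpha at .05) yields a sample of N=25". The SAP then concedes: "This leaves open the issue of power for neural measures". It answers with EEG and sEEG pilot figures and concludes that "this sample size will be more than sufficient for sEEG measures, especially as they will be utilized in a within-patient/within-electrode experimental design".
- **Behaviour** (SAP, Behavioral Analyses). Patient is a random effect in the mixed logistic models.
- **Encoding models** (SAP, Neural Analyses). "For a given electrode, individual models will be built using single trial data and a sliding window". The null distribution for the F-statistic comes from shuffling trials.
- **Noise** (SAP, Neural Analyses). A channel/timepoint significant in either Baseline or Noise has its coefficient t-statistics compared between the two contexts. The expectation is that "encoding of F0 will strengthen and VOT will weaken in Noise, as measured by changes in *t*-statistic magnitudes across multiple models". No test, unit or threshold follows.
- **Canonical and Reverse** (SAP, Neural Analyses). The cluster test is limited to Baseline-significant channels and windows and works by "randomly assigning listening context labels to single-trial data followed by a *t*-test at each time step".
- **Multiplicity** (SAP, Rigor and Reproducibility). Control for multiple comparisons and a sex covariate are promised, without a method or level.

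**The concern.** H1 to H4, and the neural predictions that accompany H5, are statements about how cortex responds, and the study recruits 25 patients to support them. To generalise to patients, a context effect must be judged against its variation between patients. The behavioural models contain that term. The neural analyses have no patient term, no aggregation step and no rule for turning channel results into a conclusion about a hypothesis.

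Two consequences follow. First, a patient with many auditory contacts can contribute many significant channels, and nothing in the plan limits that patient's weight. Second, the analyst must choose the unit for the Noise comparison later. The unit nearest to hand is the channel-by-window model. Such models are unlikely to be independent: neighbouring windows of one channel are serially correlated, and channels in one patient share trials and patient state. Treating them as independent would understate the standard error.

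**Working it through.** **1. The plan's own figure.** N = 25 cannot be reproduced, because the behavioural effect size is given only in a figure. Solving backwards for a paired or one-sample t-test (two-sided .05, power 0.80), the normal approximation is (1.960 + 0.842)/√25 = 0.560, and the noncentral t gives 0.584 between-patient SD. This is an implied value, not a check of the calculation.

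**2. Units, side by side.**

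| Analysis | Observation | Patient term |
|---|---|---|
| Behavioural logistic models | classification response | random effect |
| Encoding models | single trial, one electrode and window | none |
| Noise vs Baseline | t-statistics from several models | none; no test named |
| Canonical/Reverse clusters | single trial, Baseline-significant channels | none |

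**3. If channels were pooled as independent.** Let m be channels per patient and ρ the within-patient correlation of the context change (ICC). Both are assumptions. With no true mean change, the real type I error of a nominal 5% test is 2[1 − Φ(1.96/√D)], with D = 1 + (m − 1)ρ. For m = 10 and ρ = 0.2, D = 2.8 and 1.96/√2.8 = 1.17, which gives 24%.

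| m | ρ = 0.05 | ρ = 0.5 |
|---|---|---|
| 2 | 5.6% | 11% |
| 5 | 7.4% | 26% |
| 10 | 10% | 40% |
| 20 | 16% | 55% |

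Simulation with 25 patients agrees to within about one percentage point. A t-test on 25 patient means stays at 4.6–5.3%.

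**4. If windows were pooled too.** Assume w = 10–20 windows, lag-1 correlation φ = 0.5–0.8 and m = 4–10. Serial correlation alone inflates the variance by V = 1 + 2Σ(1 − k/w)φ^k, summed over k = 1 to w − 1.
- *Independent channels.* V = 2.60 (w = 10, φ = 0.5) gives 22%. V = 7.02 (w = 20, φ = 0.8) gives 46%. Simulation over these ranges gives 20–49%.
- *Channels of a patient share 20% of the variance and patient ICC is 0.05.* Here D = 0.05mw + 0.95V(0.2m + 0.8). For m = 4, w = 10, φ = 0.5: D = 2 + 3.95 = 5.95, which gives 42%. For m = 10, w = 20, φ = 0.8: D = 10 + 18.68 = 28.68, which gives 71%. Simulation gives 42–75%.
- *Same sharing, windows averaged to one value per channel first.* Simulation gives 14–39%.
- *One value per patient.* Simulation gives 4–6%.

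These figures leave out the SAP's selection of channel/timepoints significant in either context.

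**5. The within-channel accent test.** Suppose the mean effect over patients is zero but patients truly differ, with between-patient SD equal to k times a channel's standard error (k is an assumption). A channel is then significant with probability 2[1 − Φ(1.96/√(1 + k²))]: 8%, 17% and 38% for k = 0.5, 1 and 2. These are not errors about that channel. They show that significant channels alone do not establish a mean effect over patients.

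**6. What a patient-level test can detect.** At 80% power and two-sided .05, by noncentral t: 0.58 SD with 25 contributing patients, 0.66 with 20, 0.78 with 15 and 1.00 with 10.

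**The case against.** The strongest reply is that the SAP never says models will be pooled. The change in t-statistics may simply mean Baseline against Noise for the same channel, or over its successive windows. This stands. A reader might infer that the Noise test is known to be too liberal, but the documents name no test, so its error rate is undefined. The 20–75% figures describe a pooled t-test that the plan does not propose, with inputs it does not give.

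A reader might also infer that the cluster test is invalid. It is not: permuting labels over trials is sound for the channel in question if trials are exchangeable, and the SAP openly describes a "especially as they will be utilized in a within-patient/within-electrode experimental design". That the test runs separately in each channel is itself only the natural reading. If trials were pooled over channels or patients, patient would still not be the unit.

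Nor does it follow that recruiting 25 patients adds nothing. Similar channel effects recurring across patients are informal replication. But the plan gives no rule for weighing them.

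Three other defences are weaker. Multiplicity control addresses how many tests are run, not the clustering of their units. Sex is constant within a patient, so it implies some between-patient model, but none is described. The pre-registered analyses that the SAP mentions might supply the missing step, but they are not in these documents.

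**Conclusion.** The concern holds as a gap in the plan. Followed as written, the SAP never tests a neural context effect over patients, although it sets out that structure for behaviour. The conclusion rests on the text alone. The size of any inflation rests on assumed channel counts, window counts and correlations, and on an assumed pooled test; within those assumptions it runs from slight (5.6%, two weakly correlated channels per patient) to severe (about 75%). The direction does not depend on the exact values: positive correlation within patients or between windows makes pooling anti-conservative.

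It would also go too far to say that the study has 80% power at 0.58 SD for its neural measures. That figure needs all 25 patients to contribute usable channels, whereas the protocol (Study Design, item 2) and the SAP (Statistical Design, Power and Analytic Approach) make task completion conditional on the patient. This should be fixed before the neural data are analysed. It does not invalidate the design.

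**What to change.** 1. **SAP, Neural Analyses.** For each neural context hypothesis, add a patient-level test. One option is a single mean context contrast per patient, over supratemporal-plane contacts and windows specified in advance and not chosen from the contrast being tested, with a sign-flip permutation test over patients. The other is a mixed model with random effects for patient and for channel within patient. State that this test decides the hypothesis.
2. **Same section.** Keep the per-electrode encoding models and cluster tests as channel-level maps of where and when effects occur.
3. **SAP, Power and Sample Size.** Replace the sufficiency claim for sEEG with the detectable effects at 80% power and two-sided .05, by number of patients with usable channels: 0.58, 0.66, 0.78 and 1.00 between-patient SD for 25, 20, 15 and 10 patients.

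The cost is SAP wording and one further analysis step on data already planned. The downside is that p-values and stated power will look less favourable than channel-level ones.
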